# 7.0 Assessment of Safety and Effectiveness

# 7.1 Primary Safety Endpoint

Amputation-Free Survival at 30 days, defined as the percentage of subjects with:

- Limb Salvage: Freedom from above-ankle amputation of the index limb AND
- **Survival**: Freedom from all-cause mortality

# 7.2 Secondary Safety Endpoint

Amputation-Free Survival at 6 months, defined as the percentage of subjects with:

- Limb Salvage: Freedom from above-ankle amputation of the index limb AND
- **Survival:** Freedom from all-cause mortality

# 7.3 Secondary Effectiveness Endpoints

There are multiple secondary effectiveness endpoints to be evaluated in the study:

- **Primary Patency at 30 days**: Defined as the absence of total occlusion of the stent graft without prior clinically driven major re-intervention of the stent graft at 30 days.
- **Primary Patency at 6 months**: Defined as the absence of total occlusion of the stent graft without prior clinically driven major re-intervention of the stent graft at 6 months.
- Secondary Patency at 6 months: Defined as the absence of total occlusion of the stent graft with or without prior clinically-driven major re-intervention of the stent graft at 6 months.

• **Deterioration in Renal Function at 6 months:** Defined as a 25% increase in serum creatinine after using iodine contrast agent without another clear cause for kidney injury.

• Limb Salvage at 3, 6, 9, and 12 months: Defined as percentage of subjects with freedom from above-ankle amputation of the index limb.

• Wound Healing at 3, 6, 9, and 12 months: Defined as percentage of subjects with completed index wound healing.

• Technical Success: Percentage of technical success, defined as completion of the endovascular procedure and immediate morphological success with successful placement of the arterial and venous catheters in the desired location in the limb, and ability to place the stent graft.

• **Procedural Success:** Percentage of subjects with a procedural success, defined as combination of technical success, and absence of all-cause mortality, above-ankle amputation or clinically-driven major re-intervention of the stent graft through 30 days.

 Occlusion is defined as absence of flow on color Doppler, and/or absence of flow on angiographic images (conventional or CT).

 Clinically-driven major re-intervention is defined as the creation of a new surgical bypass, the use of thrombectomy or thrombolysis (i.e., procedures done in the setting of lost primary-assisted patency), or major surgical revision such as a jump graft or an interposition graft performed for critical occlusion of the stent graft.

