## 5.1.1. Pre-operative Inclusion Criteria

- 1. Subject must be  $\geq$  21 and  $\leq$  95 years of age
- 2. Clinical diagnosis of symptomatic critical limb ischemia, defined as any of the following clinical assessments coupled with hemodynamic evidence of severely diminished arterial inflow of the index limb (e.g., absent pulse(s), TcPO2 < 30 mm Hg):
  - a. Rutherford Classification 5, ischemic ulceration
  - b. Rutherford Classification 6, severe ischemic ulcers or frank gangrene
- 3. Subject has been assessed by the principal investigator, and reviewed by the Independent Safety Committee (ISC), and it was determined that no conventional distal bypass surgical or endovascular therapy for limb salvage is feasible due to the absence of a suitable distal target artery.
- 4. Proximally, the Target In-flow Artery at the cross-over point must be treatable with a 3.5– 4.0 mm stent after pre-treatment (by visual estimate), and be <50% stenosed
- 5. Prior stent(s) to the Target In-flow Artery are allowed

- 6. Planned minor amputation of target extremity within 30 days after the index procedure is allowed
- 7. Subject is willing and able to sign the informed consent form
- 8. Subject has an adequate support network to ensure that subject is compliant with medication regimen and follow-up study visits

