## 6.3. Visit Schedule

The study coordinator at the site should schedule the 30-day follow-up visit before the subject is discharged post-procedure. Obtain contact information for subject's significant other or caretaker(s) to ensure that subject will be able to comply with follow-up study visits. Study assessments to be performed at each visit are summarized in Table 1.

TABLE 1: Study Assessment Schedule	Visit 1 Day -1 -21 to -2 (Screen- ing & Baseline)	Visit 2 Day 0 (Treat- ment- dis charge)	Visit 3 30 (+/- 7) Days	Visit 4 60 (+/- 7) Days	Visit 5 (3 mo. +/- 2 wks) & Visit 7 (9 mo. +/- 2 wks)	Visit 6 6 months (+/- 2 weeks)	Visit 8 1 Year (+/- 4 weeks)	Visit 9  2 Year (+/- 4 weeks)
Written Informed Consent	1							
Baseline angiogram/images for screening	1							
Inclusion / Exclusion criteria assessment, including enrollment concurrence by an Independent Safety Committee that subject is not a candidate for conventional surgical or endovascular limb salvage procedures	1							
Demographic data, medical history, medication review, & physical exam	1							
Review of medications / dual anti-platelet regimen 	V	V	$\checkmark$		V	1	1	V
Rutherford Classification (RCC)	1		$\checkmark$		1	V	1	1
Wound healing assessment (completed or not), and photographs 	V		$\checkmark$		1	$\checkmark$	1	V
Index limb oxygenation measurement – TcPO2 	V		$\checkmark$		1	$\checkmark$	1	
Pulse evaluation via continuous wave doppler assessment of grafted area (proximal, graft, and distal to outflow vessels) 	√ (target location)	√8	~		1	V	V	1

TABLE 1: Study Assessment Schedule (cont)	Visit 1 Day -1 -21 to -2 (Screen- ing & Baseline)	Visit 2 Day 0 (Treat- ment- discharge )	Visit 3 30 (+/- 7) Days	Visit 4 60 (+/- 7) Days	Visit 5 (3 mo. +/- 2 wks) & Visit 7 (9 mo. +/- 2 wks)	Visit 6 6 months (+/- 2 weeks)	Visit 8 1 Year (+/- 4 weeks)	Visit 9  2 Year (+/- 4 weeks)
Serum Creatinine	√		$\checkmark$			$\checkmark$		
Numeric Pain Scale Rating (1-10) 	1		1		1	1	1	V
Procedural angiogram and device performance data		V						
Technical Success		4						
Procedural Success		1	1					
Procedure time, defined from sheath insertion to final catheter removal		V						
Fluoroscopy time and Contrast Load for the index procedure		V						
Device- or procedure-related AE/SAE's 		1	V		1	$\checkmark$	1	$\checkmark$

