# 6.6 Study Exit

Once the subject has a) completed the follow-up visits; b) has withdrawn consent to participate in the study; c) has met a primary study endpoint, or d) was enrolled but not able to have the device implanted, they will be exited from the study provided they do not have any conditions that require continued follow-up. The date of exit, reason, and subject status should be recorded.

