## 8.1.3. Missing Data

Missing data will not be imputed by any method. All subject data will be collected on standardized case report forms.

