# 10.2. Independent Safety Committee (ISC)

An Independent Safety Committee will act as the medical monitor for this early Pilot Study. The ISC will consist of at least two (2) physicians with experience in surgical and/or endovascular treatment of CLI patients, who are independent from the Sponsor and are not investigators in the study. Whenever possible, the ISC will review data in a blinded fashion (i.e., blinded to site and subject ID, follow-up period, etc.) to minimize any potential bias. Specific roles, responsibilities and processes will be described in a Safety Charter, which will be agreed upon by ISC members and published prior to commencement of the study.

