#### **Endpoint Assessment/Adjudication:**

**Technical Success:** The ISC will review the procedural angiograms to assess stent graft/limb patency post-procedure to determine Technical Success.

**Outcomes Adjudication**: Reports of endpoint events will be reviewed and adjudicated, including but not limited to:

- Major amputation of the index limb
- Stent graft occlusion and/or acute stent thrombosis (via DUS and/or angiographic documentation)
- Death
- Major and minor re-interventions of the index limb
- Contrast-induced nephropathy
- Wound healing (progression, completion, confirmation).

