#### AMPUTATION

*Major amputation* is defined as amputation of the index limb at the level above the ankle.

*Minor amputation* is defined as amputation(s) of the index limb/metatarsals at the level below the ankle. Indication for minor amputations should be documented in the CRF.

**Pre-planned amputation** is defined as minor amputation(s) that are prospectively anticipated as part of the overall procedure and care plan for a subject. These anticipated procedures should be documented in the medical record prior to the index procedure.

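### Wound Healing does not say how a subject with a major amputation is scored, and the exit and no-imputation rules can drop these known failures from the denominator

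*Combined protocol and SAP*

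**What the plan says.** The Wound Healing endpoint in section 7.3, repeated in the synopsis, is "Defined as percentage of subjects with completed index wound healing" at 3, 6, 9 and 12 months. Neither the index wound nor completed healing is defined in 7.3, the synopsis or the section 16.0 glossary. Table 1 (section 6.3) lists the assessment as "Wound healing assessment (completed or not), and photographs", with no category for a wound that is no longer there.

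Four provisions bear on a subject with a major amputation:

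- Section 7.1 makes above-ankle amputation of the index limb one of the two failure components of the primary endpoint, 30-day amputation-free survival.
- Section 6.6 exits a subject who "has met a primary study endpoint", unless a condition needs continued follow-up. The synopsis uses similar terms for closing the study.
- Section 8.1.3 states: "Missing data will not be imputed by any method".
- Section 8.1.2 puts eligible, implanted subjects in the Per Protocol effectiveness set. It does not say how to score someone with no limb to examine.

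On minor amputation, section 5.1.1 states: "Planned minor amputation of target extremity within 30 days after the index procedure is allowed". The glossary describes pre-planned amputation as "minor amputation(s) that are prospectively anticipated as part of the overall procedure and care plan for a subject" but does not link it to wound status. Section 10.2 assigns adjudication of wound healing to the ISC and adds: "Specific roles, responsibilities and processes will be described in a Safety Charter". That charter is not among the documents.

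**The concern.** A subject whose index limb is amputated above the ankle has failed treatment, and the failure is known. Such a subject should count against the healing rate at every later visit. The plan does not say so. If the subject is exited, no later wound assessment exists. If the subject stays in follow-up, there is no wound to mark. Either way the field may be blank, and an analyst applying 8.1.3 may treat a blank as missing and leave the subject out.

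That would remove some of the clearest failures from the denominator while keeping every success in the numerator. The study is single-arm, so no comparator would show the shift, and section 1.3.2 presents improved wound healing as the benefit that justifies the risks.

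A second, smaller gap concerns minor amputation. It is permitted within 30 days, before the first healing time point at 3 months. If the operation removes the index wound, the protocol does not say whether the amputation site takes its place.

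**Working it through.** **No figure to reproduce.** The documents give no expected healing rate, target, alpha or power. Section 8.3 rests the sample size on a convention of at least 10 completed subjects. The check is therefore a reading of the rules, followed by a sensitivity calculation.

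**Rules side by side.** Procedural Success in 7.3 names death, above-ankle amputation and major re-intervention as failures. Primary patency treats a prior major re-intervention as a failure. Wound Healing names no intervening event. Taking 7.1, 6.6 and 8.1.3 in sequence: amputation is a component of the primary endpoint, meeting that endpoint leads to exit, and no value is filled in afterwards. One link is uncertain. The primary endpoint is set at 30 days, and 6.6 does not say whether an amputation at, say, month 4 also triggers exit. If it does not, the subject stays in follow-up with nothing to assess, and scoring is still undefined.

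**Formula.** Let N be the effectiveness set, M the major amputees by the time point, and H the subjects healed, none of them a major amputee.

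- Amputees kept as not healed: H/N
- Amputees dropped: H/(N − M)
- Ratio of the two: N/(N − M), whatever H is

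**Inputs.** N = 35 is the enrolment ceiling in 4.2; the Per Protocol set may be smaller. H is assumed throughout. In the first row M = 7 is also assumed. In the other rows M comes from the surgical meta-analysis quoted in 1.1, which gives 71% one-year foot preservation (95% CI 64–77%):

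- 35 × 0.29 = 10.15, about 10
- 35 × 0.23 = 8.05, about 8
- 35 × 0.36 = 12.6, about 13

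Those series are of a different procedure, so this only sets a plausible scale for the 12-month time point.

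| H | M | Kept | Dropped | Difference (points) |
|---|---|---|---|---|
| 14 | 7 | 14/35 = 40.0% | 14/28 = 50.0% | 10.0 |
| 10 | 8 | 10/35 = 28.6% | 10/27 = 37.0% | 8.5 |
| 10 | 10 | 10/35 = 28.6% | 10/25 = 40.0% | 11.4 |
| 10 | 13 | 10/35 = 28.6% | 10/22 = 45.5% | 16.9 |
| 16 | 8 | 16/35 = 45.7% | 16/27 = 59.3% | 13.5 |
| 16 | 10 | 16/35 = 45.7% | 16/25 = 64.0% | 18.3 |
| 16 | 13 | 16/35 = 45.7% | 16/22 = 72.7% | 27.0 |

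With M = 7 the ratio is 35/28 = 1.25; with M = 10 it is 35/25 = 1.40.

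Exact 95% intervals with M = 10 are 14.6–46.3% (kept) against 21.1–61.3% (dropped) for H = 10, and 28.8–63.4% against 42.5–82.0% for H = 16. They overlap, as they must at this size, but the shift is systematic and the intervals do not reflect it.

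**Minor amputation.** Each subject with an open amputation site who is counted as healed adds 1/35 = 2.9 points. The documents give no basis for how many there might be.

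**The case against.** The strongest reply is that 7.3 speaks of a percentage of subjects and 8.1.2 includes all eligible implanted subjects. A major amputation is a known, adjudicated outcome. On that reading the subject stays in the set without completed healing, and 8.1.3 has nothing to act on, because it concerns missing values and not known failures. This is a fair reading, and it is why the bias is possible and not certain. It does not close the gap: 8.1.2 defines who is in the set, not how an exited amputee is scored, and 6.6 points the other way.

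Limb Salvage is also reported at the same four time points, so amputations would not be hidden. That helps a careful reader but does not fix the denominator of the healing rate.

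On minor amputation the reply largely stands. A reader might infer that sites decide for themselves whether a removed wound is healed. The documents do not support that: the ISC adjudicates healing (10.2), and 6.5 requires photographs of the dorsum with toes, both sides and the sole, so an open amputation site should be visible. The Safety Charter may also hold a rule. What remains is a definition missing from the protocol text.

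Two further inferences go too far. One is that every reading the text permits raises the rate. It equally permits following the amputation site and counting major amputees as not healed, and neither inflates anything. The other is that better scoring would allow healing to be attributed to the arterialised circulation. In a single-arm study where minor amputation may be part of the care plan, it would not.

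**Conclusion.** The concern holds for major amputation. The protocol does not state how these subjects are scored for Wound Healing, and a literal reading of 6.6 with 8.1.3 can remove them from the denominators at 3 to 12 months. In the illustration the rate becomes 50% instead of 40%. With amputation counts scaled from the cited meta-analysis and an assumed 10 or 16 healed wounds, the difference is 8.5 to 27.0 points. All of this rests on assumed healed counts, on a set of 35, and on all major amputees being dropped; under the inclusive reading of 8.1.2 the difference is zero.

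The endpoint is a descriptive secondary one with no test or performance goal. What is affected is how the rate can be interpreted, not type I error or power. The minor-amputation part is a secondary clarification.

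**What to change.** 1. In 7.3, state that a subject with a prior above-ankle amputation of the index limb is counted as not healed at every later time point and stays in the effectiveness denominator.
2. In 8.1.3, state that this is a known outcome and not imputation, and that it applies whether or not the subject has been exited under 6.6.
3. As a secondary clarification, state for ISC adjudication that when a minor amputation removes the index wound, the amputation site is assessed as the index wound and must be closed to count as completed healing. Check the Safety Charter first and align the two.

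Death before a visit raises a similar denominator question, and the same paragraph can say how it is handled. Reporting healing separately by minor amputation is optional in a study of at most 35 subjects.

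The cost is small. Amputation assessments and photographs are already collected, so the change is text in the protocol, with matching wording in the case report form guidance and the charter. The downside is a somewhat lower reported healing rate than if amputees were dropped. The change concerns only how outcomes are classified, not how patients are treated.

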# **8.0 Statistical Considerations**

## 8.1 Analysis Populations and Data Handling Conventions

## 8.1.1. Safety

All subjects who receive any portion of the LimFlow Stent Graft System will be included in safety analysis, as Intent to Treat population (ITT).

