## 6.4 Study Procedures

#### 6.4.1 Enrollment

Once any component of the LimFlow Stent Graft System is introduced into the body, the subject will be considered to be enrolled in the study and subject to all follow-up requirements. If the device is introduced but implantation is either not attempted or unsuccessful, subjects will be followed through 30 days for safety only, or through resolution or stabilization of any device- or procedure- related adverse events, whichever is longer. Those subjects will then be exited from the study and will not be replaced.

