#### 6.4.2. Intra-operative

At a minimum, all subjects must be started on dual anti-platelet therapy (DAPT) at least 1 week before the procedure or adequately pre-loaded with DAPT according to the institution's practice. For consented subjects that meet the pre-operative eligibility criteria, record the relevant data regarding their endovascular procedure. Record the following information:

- Target In-Flow Artery (cross-over point), including proximal reference vessel diameter (RVD) and assessment of calcification or any other abnormalities
- Target Out-Flow Vein (cross-over point) characteristics
- Intra-operative anticoagulants administered, and corresponding ACT levels
- Pre- and post-procedural angiographic images showing flow to the foot
- Procedure start and finish times
- Total contrast amount given
- Total fluoroscopy time for the procedure
- Documentation of any device- or procedure-related adverse events
- Technical Success

At the end of the endovascular procedure, with the procedural sheath in place and under fluoroscopic visualization, an injection of contrast will be made to assess the anatomy, placement and patency of the proximal, body and distal ends of the Stent Graft.

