# **11.2.** Reporting of Serious and Non-Serious Adverse Events

## 11.2.1. General Reporting Requirements (Serious & Non-Serious Adverse Events)

All potentially device- and/or procedure-related adverse events (AE) and all serious adverse events (SAE) will be reported and monitored from the time of treatment through the 6 month follow-up visit. Any SAEs related to the index limb will be reported and monitored throughout the 2 year follow-up visit. The report should include: severity, duration, action taken, treatment outcome and

relationship of the adverse experience to the study device, procedure, concomitant medications, preexisting condition, etc. (i.e., unrelated, related or relationship unknown).

In the case of serious adverse events, procedure and/or device observations and malfunctions, medical record documentation (e.g. procedure notes, operative notes, discharge summary, relevant progress notes, imaging or lab studies) must be provided to sponsor or its designee.

The following criteria must also be adhered to by the investigator in the case of serious adverse events:

- The Adverse Event eCRF must be signed by the investigator.
- It is the responsibility of the investigator to inform their IRB of serious adverse events as required by their IRB procedures and in conformance with FDA and local regulatory requirements.

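### The safety set labelled intent to treat starts at first device introduction, so harm during required pre-procedure antiplatelet therapy has no clear collection window and feasibility has no attempt-based denominator

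*Combined protocol and SAP*

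**What the plan says.** - **Safety set (8.1.1).** "All subjects who receive any portion of the LimFlow Stent Graft System will be included in safety analysis, as Intent to Treat population (ITT". Under 8.2.2.1 this set carries the primary endpoint, 30-day amputation-free survival.
- **Enrollment (6.4.1).** "Once any component of the LimFlow Stent Graft System is introduced into the body, the subject will be considered to be enrolled in the study". The 30-day safety follow-up for failed or unattempted implants applies only after that point.
- **Required earlier step (6.4.2 and footnote 1 of Table 1).** "all subjects must be started on dual anti-platelet therapy (DAPT) at least 1 week before the procedure or adequately pre-loaded with DAPT", following institutional practice.
- **Adverse event capture.** Section 11.1 first defines an adverse event broadly, then ties the definition to onset after the study procedure or worsening of baseline disease after it. Section 11.2.1 has device- or procedure-related events and all serious events reported "from the time of treatment through the 6 month follow-up visit". Time of treatment is not defined. The adverse event row of Table 1 has no mark at Visit 1.
- **Recording at the procedure (6.4.2).** Procedural data, including device- or procedure-related adverse events and Technical Success, are to be recorded for consented subjects who meet the pre-operative criteria. That group is wider than the enrolled.
- **Feasibility results.** Technical and Procedural Success are secondary effectiveness endpoints (7.3). Section 8.2.3.1 summarizes those endpoints in the 8.1.2 set: enrolled subjects who meet all criteria and are implanted. The proportion converted to other treatment is limited to LimFlow subjects.

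**The concern.** Feasibility and safety are both stated objectives (3.0). A reader who sees intent to treat will assume that the set holds everyone for whom treatment was intended. It holds those in whom a component was introduced.

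Two things are at stake. First, the protocol requires a medication before the procedure, but its adverse event rules start at or after the procedure. A serious bleed during that period could go uncollected by a site that follows the text. Second, a procedure abandoned before any component is introduced appears in no planned rate, so the feasibility figures are conditional on having passed that stage. In a pilot of at most 35 subjects a few such stops matter, and the planned tables would not show how many there were.

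**Working it through.** The plan has no figure to reproduce here. Section 8.3 rests on a convention of 10 completed subjects and gives no target rate, power or margin. The check is a comparison of definitions, followed by an illustration of size.

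**Step 1: follow two subjects through the text.**

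*Subject A* is consented and approved by the Independent Safety Committee, starts the required antiplatelet therapy, has a serious bleed, and never reaches the procedure.
- Enrolled? No (6.4.1).
- In the safety set? No (8.1.1).
- Collected as an adverse event? Unclear. The broad first sentence of 11.1 and its statement that all serious events are reported point to yes. The onset rule in 11.1, the start point in 11.2.1 and Table 1 point to no.

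*Subject B* is brought to the procedure, which stops before any component is introduced.
- Enrolled, or in the safety or effectiveness set? No.
- Data recorded? Yes, on a plain reading of 6.4.2.
- Counted in a planned rate? No. Sections 8.1.1 and 8.1.2 govern the rates and exclude this subject.

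**Step 2: size for feasibility.** Inputs: 35 enrolled, the maximum in 4.2. Assumptions: all 35 are implanted with technical success, and k further attempts stop before device introduction. The documents give no value for k. Rate over attempts = 35/(35 + k). Exact 95% limits for x out of n: lower = Beta quantile 0.025 with parameters (x, n − x + 1); upper = Beta quantile 0.975 with parameters (x + 1, n − x). For x = n the upper limit is 100%.

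| k | Technical Success over attempts | Exact 95% CI |
|---|---|---|
| 0 (equals the planned rate) | 35/35 = 100% | 90.0 to 100 |
| 1 | 35/36 = 97.2% | 85.5 to 99.9 |
| 3 | 35/38 = 92.1% | 78.6 to 98.3 |
| 5 | 35/40 = 87.5% | 73.2 to 95.8 |

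Each stop costs about 2.5 to 2.8 points: 100 − 97.2 = 2.8 for the first, and (100 − 87.5)/5 = 2.5 on average over five.

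**Step 3: the planned denominator also drops enrolled failures.** Suppose 3 of 35 enrolled subjects are not implanted, and the other 32 meet all criteria and are technical successes. The planned rate is 32/32 = 100% (89.1 to 100). Over all enrolled it is 32/35 = 91.4% (76.9 to 98.2). With 3 earlier stops as well, it is 32/38 = 84.2% (68.7 to 94.0) of attempts. A rate among implanted subjects is close to 100% by construction.

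**Step 4: size for the primary endpoint.** Assume 33/35 = 94.3% (80.8 to 99.3) and three omitted subjects.
- None has an event: 36/38 = 94.7% (82.3 to 99.4).
- One has an event: 35/38 = 92.1% (78.6 to 98.3).
- All three have events: 33/38 = 86.8% (71.9 to 95.6).

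**The case against.** **The set is conventional and its membership is explicit.** An exposure-based safety set is usual in a single-arm device pilot, and here it equals all enrolled subjects. This stands. The set should stay; renaming it alone would only change a label.

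**Early events are not wholly ignored.** Section 6.4.2 records events for consented, eligible subjects. The adverse event summary in 8.2.2.2 names no analysis set. Section 10.1.1 has serious procedural complications analyzed individually and evaluated by the committee. Section 11.1 counts medications required for the procedure among the causes of procedure-related events. Table 1 times the procedure from sheath insertion. This also stands. A reader might infer that subjects stopped early have no adverse event reporting and appear in no safety or feasibility result. The documents do not support anything so absolute: they are inconsistent about who is recorded. But recording is not analysis, and none of these provisions supplies a denominator or a clear start date for events during pre-procedure therapy.

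**In-flow artery pre-treatment.** A reader might also infer that pre-treatment is a second required step before device entry, at which anatomy excludes subjects. The documents do not say so. It appears only in inclusion criterion 4 ("stent after pre-treatment (by visual estimate), and be <50% stenosed"), a pre-operative criterion that Table 1 has assessed at Visit 1. Section 6.4.2 does not list it as a step, and its order relative to device introduction is not stated. No part of this point rests on it.

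**The number of early stops is unknown.** True. It may be zero, and then no rate changes.

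**Conclusion.** The point holds in two parts.

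1. *Safety capture.* Antiplatelet therapy is required before enrollment, while the adverse event rules start at or after the procedure or treatment. A serious event in between has no clear collection window. If the subject then receives no component, that subject is also outside the primary endpoint's denominator. This rests on the text alone.
2. *Feasibility.* No planned rate uses attempted subjects, and Technical Success is computed only among the implanted. Under the assumed counts of 1 to 5 early stops, the rate over attempts is 97.2% to 87.5%, against a planned 100%.

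The intent-to-treat label is a misnomer that hides both gaps but is not itself the harm. It would be wrong to conclude that the primary result is materially biased: 30-day amputation-free survival barely moves unless an omitted subject dies or has a major amputation. The change is worth making because it is cheap and feasibility is a stated objective.

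**What to change.** 1. In 8.1.1, rename the set the enrolled/treated safety set. Its membership does not change.
2. In 8.2, add one table for all consented, committee-approved subjects brought to the procedure: number attempted; number stopped before device introduction, with reasons; their recorded adverse events; and Technical Success over all attempted and over all enrolled subjects, beside the planned rate among the implanted.
3. In 11.1 and 11.2.1, start serious adverse event collection at the first protocol-required pre-procedure medication or procedure after consent, and define the time of treatment. List separately any serious events in subjects who never reach the procedure.
4. Align 6.4.1, 6.4.2, 8.1.1, 11.1, 11.2.1 and the adverse event row of Table 1, so that the group recorded and the group reported agree.

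The cost is wording, one table and a few extra serious adverse event forms. Section 6.4.2 already calls for procedural data on consented, eligible subjects, and 14.2 already requires source documents for those screened. The downside is a possibly lower reported feasibility rate. Treatment, eligibility and sample size are unchanged.
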